10.2. Appendix 2: Clinical Laboratory Tests

- The tests detailed in [Table 10](#) will be performed by the local laboratory.
- Protocol-specific requirements for inclusion or exclusion of participants are detailed in [Section 5](#) of the protocol.
- Additional tests may be performed at any time during the study as determined necessary by the investigator or required by local regulations.
- Pregnancy Testing
 - Refer to [Section 5.1](#) Inclusion Criteria for screening pregnancy criteria.
 - Pregnancy testing should be conducted at the time points indicated in the SoA (see [Section 1.3](#)).
 - Additional serum or urine pregnancy tests may be performed, as determined necessary by the investigator or required by local regulation, to establish the absence of pregnancy at any time during the participant's participation in the study.

Table 10 Protocol-Required Safety Laboratory Assessments

Laboratory Assessments	Parameters		
Hematology	Platelet Count Red Blood Cell Count Hemoglobin Hematocrit	Red Blood Cell Indices: Mean corpuscular volume Mean corpuscular hemoglobin	White blood cell count with differential: Neutrophils Lymphocytes Monocytes Eosinophils Basophils
Clinical Chemistry ¹	Blood urea nitrogen Creatinine Glucose (fasting) Potassium Sodium Magnesium	Aspartate aminotransferase Alanine aminotransferase Alkaline phosphatase Total and direct bilirubin Creatine phosphokinase Calcium	Chloride Carbon dioxide Total protein Albumin
Routine Urinalysis	
 • Specific gravity • pH, glucose, protein, blood, ketones, bilirubin, urobilinogen, nitrite, and leukocyte esterase by dipstick • Microscopic examination (if blood, leukocyte esterase, or protein is abnormal) 		

Laboratory Assessments	Parameters
Other Screening Tests	
 • Serology: HIV-1 and -2 antigen/antibody immunoassay, Hepatitis B surface antigen (HBsAg), Hepatitis C (Hep C antibody) • Alcohol, cotinine, and drug screen (to include at minimum amphetamines, barbiturates, cocaine, opiates, cannabinoids, and benzodiazepines) • Pregnancy • Follicle-stimulating hormone • Fecal occult blood test and stool cultures as appropriate for gastrointestinal adverse events (Appendix 7).

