8.3. Clinical Laboratory Analyses

Laboratory evaluations including the analyses of chemistry laboratory tests, hematology laboratory tests, urinalysis, and liver function tests will be based on GSK Core Data Standards. Division of Microbiology and Infectious Diseases (DMID) grading for all parameters as specified in the protocol will be assigned programmatically by PPD in the Laboratory Analysis Dataset. The details of the planned displays are in [Appendix 10: List of Data Displays](#).

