10.7.1. Laboratory Values

Parameter values are converted to use SI units.

HEMATOLOGY				
	Grade 1	Grade 2	Grade 3	Grade 4
Hemoglobin	9.5 to 10.5 gm/dL	8.0 to 9.4 gm/dL	6.5 to 7.9 gm/dL	<6.5 gm/dL
Absolute Neutrophil Count	1000 to 1500 /mm ³	750 to 999 /mm ³	500 to 749 /mm ³	<500 /mm ³
Platelets	75,000 to 99,999 /mm ³	50,000 to 74,999 /mm ³	20,000 to 49,999 /mm ³	<20,000 /mm ³
White Blood Cells	11,000 to 13,000 /mm ³	13,000 to 15,000 /mm ³	15,000 to 30,000 /mm ³	>30,000 or <1000 /mm ³
% Polymorphonuclear Leukocytes + Band Cells	>80%	90 to 95%	>95%	N/A
Abnormal Fibrinogen	Low: 100 to 200 mg/dL High: 400 to 600 mg/dL	Low: <100 mg/dL High: >600 mg/dL	Low: <50 mg/dL High: N/A	Fibrinogen associated with gross bleeding or with disseminated coagulation
Fibrin Split Product	20 to 40 mcg/mL	41 to 50 mcg/mL	51 to 60 mcg/dL	>60 mcg/dL
Prothrombin Time (PT)	1.01 to 1.25 × ULN	1.26 to 1.5 × ULN	1.51 to 3.0 × ULN	>3 × ULN
Activated Partial Thromboplastin (APTT)	1.01 to 1.66 × ULN	1.67 to 2.33 × ULN	2.34 to 3 × ULN	>3 × ULN
Methemoglobin	5.0 to 9.9%	10.0 to 14.9%	15.0 to 19.9%	>20%

N/A=not applicable; ULN=upper limit of normal.

CHEMISTRIES				
	Grade 1	Grade 2	Grade 3	Grade 4
Hyponatremia	130 to 135 mEq/L	123 to 129 mEq/L	116 to 122 mEq/L	<116 mEq/L or abnormal sodium with mental status changes or seizures
Hypernatremia	146 to 150 mEq/L	151 to 157 mEq/L	158 to 165 mEq/L	>165 mEq/L or abnormal sodium with mental status changes or seizures
Hypokalemia	3.0 to 3.4 mEq/L	2.5 to 2.9 mEq/L	2.0 to 2.4 mEq/L or intensive replacement therapy of hospitalization required	<2.0 mEq/L or abnormal potassium with paresis, ileus, or life-threatening arrhythmia
Hyperkalemia	5.6 to 6.0 mEq/L	6.1 to 6.5 mEq/L	6.6 to 7.0 mEq/L	>7.0 mEq/L or abnormal potassium with life-threatening arrhythmia
Hypoglycemia	55 to 64 mg/dL	40 to 54 mg/dL	30 to 39 mg/dL	<30 mg/dL or abnormal glucose with mental status changes or coma

Hyperglycemia (nonfasting and no prior diabetes)	116 to 160 mg/dL	161 to 250 mg/dL	251 to 500 mg/dL	>500 mg/dL or abnormal glucose with ketoacidosis or seizures
Hypocalcemia (corrected for albumin)	8.4 to 7.8 mg/dL	7.7 to 7.0 mg/dL	6.9 to 6.1 mg/dL	<6.1 mg/dL or abnormal calcium with life-threatening arrhythmia or tetany
Hypercalcemia (corrected for albumin)	10.6 to 11.5 mg/dL	11.6 to 12.5 mg/dL	12.6 to 13.5 mg/dL	>13.5 mg/dL or abnormal calcium with life-threatening arrhythmia

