10.10.5. Safety Tables

Safety Tables					
No.	Population	IDSL / TST ID / Example Shell	Title	Programming Notes	Deliverable [Priority]
Adverse Events					
2.1	Safety	AE5B	Summary of Adverse Events by System Organ Class and Preferred Term and Maximum Grade		SAC [1]
2.2	Safety	AE5B	Summary of Drug- Related Adverse Events by System Organ Class and Preferred Term and Maximum Grade		SAC [1]
2.3	Safety	AE15	Summary of Common (>=5%) Non-serious Adverse Events by System Organ Class and Preferred Term (Number of Subjects and Occurrences)		SAC [1]
2.4	Safety	AE16	Summary of Serious Adverse Events by System Organ Class and Preferred Term (Number of Subjects and Occurrences)		SAC [1]
2.5	Safety	AE5B	Summary of Acetylcholinesterase-Inhibition Adverse Events of Special Interest by System Organ Class and Preferred Term and Maximum Grade		SAC[1]
2.6	Safety	SAFE_T1	Summary of Cumulative Grades of Acetylcholinesterase-Inhibition Adverse Events of Special Interest		SAC [1]
Laboratory Measurements					
2.7	Safety	LB1	Summary of Chemistry Change from Baseline		SAC [1]
2.8	Safety	LB1	Summary of Hematology Change from Baseline		SAC [1]
2.9	Safety	UR3	Summary of Urinalysis Dipstick Results		SAC [1]
2.10	Safety	LIVER1	Summary of Liver Monitoring/Stopping Event Reporting		SAC [1]
Electrocardiograms					
2.11	Safety	EG1	Summary of ECG Findings		SAC [1]

2.12	Safety	SAFE_T2	Summary of Frequency of Maximum Post-Dose ECG Parameter Corrected QTc Interval		SAC [1]
2.13	Safety	SAFE_T3	Summary of Frequency of Maximum Change from Baseline for ECG Parameter Corrected QTc Interval		SAC [1]
2.14	Safety	EG2	Summary of Change from Baseline in ECG Values		SAC [1]
Vital Signs					
2.15	Safety	VS1	Summary of Change from Baseline in Vital Signs		SAC [1]
Cardiovascular Risk Factors					
2.16	Safety	FH1	Summary of Family History of Cardiovascular Risk Factors		SAC [1]
2.17	Safety	SU1	Summary of Substance Use		SAC [1]

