25	Safety	SAFE_L7	Summary of Acetylcholinesterase-Inhibition Adverse Events of Special Interest by Treatment and by Maximum Grade of Each Participant	Conditional display	SAC[1]

ICH : Listings					
No.	Population	IDSL / TST ID / Example Shell	Title	Programming Notes	Deliverable [Priority]
26	Safety	SAFE_L8	Listing of Liver Adverse Events	Conditional display	SAC [1]
27	Safety	SAFE_L9	Listing of Clostridium Difficile Testing	Conditional display	SAC [1]
Laboratory Measurements					
28	Safety	LB6	Listing of Chemistry Toxicities of Grade 3 or Higher		SAC [1]
29	Safety	LB6	Listing of All Chemistry Data for Subjects with Toxicities of Grade 3 or Higher		SAC [1]
30	Safety	LB6	Listing of Hematology Toxicities of Grade 3 or Higher		SAC [1]
31	Safety	LB6	Listing of All Hematology Data for Subjects with Toxicities of Grade 3 or Higher		SAC [1]
32	Safety	UR2b	Listing of Urinalysis Toxicities of Grade 3 or Higher		SAC [1]
33	Safety	UR2b	Listing of All Urinalysis Data for Subjects with Toxicities of Grade 3 or Higher		SAC [1]
ECGs					
34	Safety	EG6	Listing of Abnormal ECG Findings		SAC [1]
35	Safety	EG6	Listing of All ECG Findings for Subjects with an Abnormal Finding		SAC [1]
36	Safety	HM10	Listing of Holter Abnormalities		SAC [1]
37	Safety	EG4	Listing of ECG Values of Potential Clinical Importance		SAC [1]
38	Safety	EG4	Listing of ECG Change from Baseline of Potential Clinical Importance		SAC [1]
39	Safety	EG4	Listing of All ECG Values for Subjects with Any Value of Potential Clinical Importance		SAC [1]

ICH : Listings					
No.	Population	IDSL / TST ID / Example Shell	Title	Programming Notes	Deliverable [Priority]
Vital Signs					
40	Safety	VS5	Listing of Vital Signs of Potential Clinical Importance		SAC [1]
41	Safety	VS5	Listing of All Vital Signs for Subjects with Potential Clinical Importance Values		SAC [1]
Liver Events					
42	Safety	LIVER5	Listing of Liver Monitoring/Stopping Event Reporting	Conditional display	SAC [1]
43	Safety	LIVER10	Listing of Hepatobiliary Laboratory Abnormalities	Conditional display	SAC [1]
44	Safety	MH3	Listing of Medical Conditions for Subjects with Liver Stopping Events	Conditional display	SAC [1]
45	Safety	MH3	Listing of Plasma Concentration Data for Subjects with Liver Stopping Events	Conditional display	SAC [1]
46	Safety	SAFE_L10	Listing of Alcohol Intake at Onset of Liver Event	Conditional display	SAC [1]
47	Safety	LIVER7	Listing of Liver Biopsy Details	Conditional display	SAC [1]

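### 14 of the 29 blood analytes in protocol Table 10 have no DMID criterion, so an isolated abnormality in one of them cannot trigger any general laboratory listing in the SAP

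*Protocol*

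**What the plan says.** Protocol Section 3 and SAP Section 2.2 name clinical laboratory tests as an endpoint of the safety objective, which is primary in both Parts. Protocol Table 10 (Appendix 2) sets the panel. Hematology includes "Platelet Count Red Blood Cell Count Hemoglobin Hematocrit" and "Mean corpuscular volume Mean corpuscular hemoglobin", plus the white cell count with five differential cell types. Chemistry includes "Total and direct bilirubin Creatine phosphokinase Calcium" and a fasting glucose.

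SAP Section 8.3 states that DMID "grading for all parameters as specified in the protocol will be assigned programmatically". The DMID laboratory tables are reproduced in SAP Appendix 7 and protocol Appendix 8.

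The planned blood-laboratory displays in SAP Appendix 10 are:

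- Tables 2.7 and 2.8, which summarize change from baseline (for chemistry, "Summary of Chemistry Change from Baseline");
- Listing 28, "Listing of Chemistry Toxicities of Grade 3 or Higher", and its hematology counterpart, Listing 30;
- Listings 29 and 31, which print the whole chemistry or hematology record of participants who have a Grade 3 or higher toxicity;
- the liver displays (Table 2.10 and Listings 42 to 48, the listings being conditional).

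SAP Appendix 6 defines values of potential clinical importance for ECG and vital signs only.

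**The concern.** The rule for showing individual laboratory results runs through the DMID grade. An analyte without a DMID row has no route of its own into the general listings, however abnormal the value. An empty or short Grade 3+ listing could then be read as showing no important laboratory abnormality, when close to half of the measured analytes could not have triggered it.

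This matters more than usual here. With about 14 active participants per Part, individual values carry most of the safety information. Part 2 is the first exposure of adolescents. Some ungraded analytes also bear on risks that the protocol itself names: Section 2.3.1 lists rash and hypersensitivity, and the liver follow-up in Appendix 6 asks for creatine phosphokinase and an assessment of eosinophilia.

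**Working it through.** The documents give no figure for this point, so the check is a count followed by a trace through the displays.

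**Step 1: match Table 10 to the DMID rows.** Hematology has 4 + 2 + 6 = 12 analytes, and chemistry has 6 + 7 + 4 = 17, with total and direct bilirubin counted separately.

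| Panel | In Table 10 | With a DMID row | Without a DMID row |
|---|---|---|---|
| Hematology | 12 | 4: platelets, hemoglobin, white cells, neutrophils | 8: red cells, hematocrit, MCV, MCH, lymphocytes, monocytes, eosinophils, basophils |
| Chemistry | 17 | 11: urea nitrogen, creatinine, glucose, potassium, sodium, magnesium, AST, ALT, alkaline phosphatase, total bilirubin, calcium | 6: direct bilirubin, creatine phosphokinase, chloride, carbon dioxide, total protein, albumin |
| Total | 29 | 15 | 14 |

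The ungraded share is 14/29 = 48% (8/12 = 67% of hematology, 6/17 = 35% of chemistry).

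**Step 2: sensitivity to how bilirubin is read.** If total and direct bilirubin are one analyte, the count is 13/28 = 46%. If the hyperbilirubinemia rows are taken to cover direct bilirubin, it is 13/29 = 45%. Creatine phosphokinase has no row under any reading.

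**Step 3: is there another criterion?** Protocol Appendix 8 gives a general severity scale for parameters outside the tables. It works by limitation of activity and need for intervention and has no numeric cut-offs, so a program cannot apply it to a laboratory value. SAP Appendix 6 has no laboratory limits.

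**Step 4: how an ungraded value can appear.**

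- Listings 28 and 30: not by its own value, because it has no grade.
- Listings 29 and 31: yes, if the same participant has a Grade 3 or higher toxicity in that panel.
- Conditional liver displays: possibly, for example direct bilirubin in Listing 43.
- Listing 17 (all adverse events): yes, if the investigator records the change as an adverse event.
- Tables 2.7 and 2.8: yes, within a group summary.

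An isolated abnormality outside the middle three routes is therefore seen only in the group summaries.

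**Step 5: low white cell count.** The DMID white cell row starts at 11,000/mm3 and otherwise grades only counts below 1000/mm3, so nothing from 1000 up to 11,000 is graded. Neutrophils are graded separately, with Grade 3 at 500 to 749/mm3 and Grade 4 below 500. A low white cell count therefore stays outside Grade 3+ when the neutrophil count is 750 or more. For example, 1500 × 0.60 = 900/mm3 is Grade 2 for neutrophils and ungraded for white cells. With no other Grade 3+ hematology result, it enters neither Listing 30 nor Listing 31.

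**Step 6: glucose.** Table 10 specifies a fasting sample. The only high-glucose row begins "Hyperglycemia (nonfasting and no prior diabetes". Glucose is counted as graded above because the hypoglycemia row applies without qualification, but the upper direction rests on a row for a different sampling condition.

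**Step 7: what a group summary shows.** As an illustration with assumed values, suppose one of 14 active participants goes from 0.5 to 10 × ULN in creatine phosphokinase and the other 13 do not change. The mean change is (10 − 0.5)/14 = 0.68 × ULN, and the SD of change is 9.5/√14 = 2.5 × ULN. The mean hides the event. The SD hints at it but does not say who had it.

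**The case against.** The strongest reply is that the investigator route is mandatory. Protocol Section 8.2.4 requires every laboratory report to be reviewed, clinically relevant changes to be recorded as adverse events, and clinically significant abnormal values to be repeated. Such an event is graded by the investigator on the general scale, which exists for this case, and reaches Table 2.1, Figure 2.3 and Listing 17. A large rise disappears from participant-level displays only if the investigator judges it not relevant. This stands, and it limits the harm. It does not replace a systematic display, because it makes reporting of a primary safety endpoint depend on case-by-case judgment for half of the panel, while ECG and vital signs have numeric limits and their own listings.

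Two further objections are partly right. The standard shells behind Tables 2.7 and 2.8 are not in the documents and may show minimum and maximum. That would reveal an extreme value, but not the participant. The 14 analytes are also not 14 independent pieces of information: hematocrit and red cell count largely follow hemoglobin, and direct bilirubin is part of total bilirubin. The share of information affected is thus smaller than 48%.

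It is also true that safety analysis is descriptive and that neither document promises shift tables or full listings. This is a gap in the displays, not a contradiction.

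A reader might infer that values of these analytes can never be flagged or listed. The documents do not support that, because of the routes in Step 4. Nor do they support the inference that any severe fall in white cells would be missed, since most such falls would also bring the neutrophil count to Grade 3.

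**Conclusion.** The point holds in a limited form. Fourteen of 29 blood analytes (13 of 28 or 13 of 29 on other readings of bilirubin) cannot by themselves bring a participant into Listings 28 to 31, because they have no DMID row and the SAP sets no other laboratory limit. Two directions of graded analytes share the weakness: white cell counts from 1000/mm3 to below the normal range, when neutrophils are 750/mm3 or more, and high fasting glucose.

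The count rests only on Table 10 and the DMID tables. How often such isolated abnormalities would occur cannot be estimated from the documents, so no probability is attached. The conclusion also assumes that Appendix 10 is the complete list of laboratory displays and that the unseen standard shells do not add a listing of out-of-range values. The primary PK results are not affected.

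**What to change.** Amend SAP Section 8.3 and Appendix 10 as follows.

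1. Keep the DMID Grade 3+ listings for the analytes that have rows.
2. Flag every Table 10 blood analyte as low, normal or high against the local laboratory reference range.
3. Add one table of the worst post-baseline shift relative to that range, by Part and treatment.
4. Add one listing of all out-of-range post-dose values for analytes, or directions, without a DMID row. Name low white cell count explicitly.
5. Flag fasting glucose against the laboratory's fasting range, and do not rely only on the nonfasting row.

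The results are already collected and no trial procedure changes. The cost is SAP wording, one table and one listing. The downside is that some trivial out-of-range values will be displayed.

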10.3. Appendix 3: Regulatory, Ethical, and Study Oversight Considerations

10.3.1. Regulatory and Ethical Considerations

- This study will be conducted in accordance with the protocol and with:
 - Consensus ethical principles derived from international guidelines including the Declaration of Helsinki and Council for International Organizations of Medical Sciences (CIOMS) International Ethical Guidelines
 - Applicable International Council for Harmonisation (ICH) Good Clinical Practice (GCP) Guidelines
 - Applicable laws and regulations
- The protocol, protocol amendments, ICF/assent form, Investigator Brochure, and other relevant documents (e.g., advertisements) must be submitted to an IRB/IEC by the investigator and reviewed and approved by the IRB/IEC before the study is initiated.
- Any amendments to the protocol will require IEC/IRB approval before implementation of changes made to the study design, except for changes necessary to eliminate an immediate hazard to study participants.
- The investigator will be responsible for the following:
 - Providing written summaries of the status of the study to the IRB/IEC annually or more frequently in accordance with the requirements, policies, and procedures established by the IRB/IEC
 - Notifying the IRB/IEC of SAE or other significant safety findings as required by IRB/IEC procedures
 - Providing oversight of the conduct of the study at the site and adherence to requirements of 21 Code of Federal Regulations (CFR), ICH guidelines, the IRB/IEC, European regulation 536/2014 for clinical studies (if applicable), and all other applicable local regulations

10.3.2. Financial Disclosure

Investigators and subinvestigators will provide the sponsor with sufficient, accurate financial information as requested to allow the sponsor to submit complete and accurate financial certification or disclosure statements to the appropriate regulatory authorities. Investigators are responsible for providing information on financial interests during the course of the study and for 1 year after completion of the study.

10.3.3. Informed Consent/Assent Process

- The investigator or his/her representative will explain the nature of the study to the participant or his/her legally authorized representative and answer all questions regarding the study.
- Participants must be informed that their participation is voluntary. Participants or their legally authorized representative will be required to sign a statement of informed consent that meets the requirements of 21 CFR 50, local regulations, ICH guidelines, Health Insurance Portability and Accountability Act (HIPAA) requirements, where applicable, and the IRB/IEC or study center.
- The medical record must include a statement that written informed consent was obtained before the participant was enrolled in the study and the date the written consent was obtained. The authorized person obtaining the informed consent must also sign the ICF.
- Participants must be re-consented to the most current version of the ICF(s) during their participation in the study.
- A copy of the ICF(s) must be provided to the participant or the participant's legally authorized representative.
- Adolescent participants should be asked for their written assent to participate in the study.
- As applicable, the IRB will be consulted before assent form development for guidance around age-appropriate groupings and any specific IRB requirements or local laws for conducting and documenting assent.
- Participants who are rescreened are required to sign a new ICF.

The ICF may contain a separate section that addresses the use of remaining mandatory samples for optional exploratory research in accordance with SOP-GSKF-410. The investigator or authorized designee will explain to each participant the objectives of the exploratory research. Participants will be told that they are free to refuse to participate and may withdraw their consent at any time and for any reason during the storage period. A separate signature will be required to document a participant's agreement to allow any remaining specimens to be used for exploratory research. Participants who decline to participate will not provide this separate signature.

10.3.4. Data Protection

- Participants will be assigned a unique identifier by the sponsor. Any participant records or datasets that are transferred to the sponsor will contain the identifier only; participant names or any information which would make the participant identifiable will not be transferred.
- The participant must be informed that his/her personal study-related data will be used by the sponsor in accordance with local data protection law. The level of disclosure must also be explained to the participant.

- The participant must be informed that his/her medical records may be examined by Clinical Quality Assurance auditors or other authorized personnel appointed by the sponsor, by appropriate IRB/IEC members, and by inspectors from regulatory authorities.

10.3.5. Publication Policy

- The results of this study may be published or presented at scientific meetings. If this is foreseen, the investigator agrees to submit all manuscripts or abstracts to the sponsor before submission. This allows the sponsor to protect proprietary information and to provide comments.
- The sponsor will comply with the requirements for publication of study results. In accordance with standard editorial and ethical practice, the sponsor will generally support publication of multicenter studies only in their entirety and not as individual site data. In this case, a coordinating investigator will be designated by mutual agreement.
- Authorship will be determined by mutual agreement and in line with International Committee of Medical Journal Editors authorship requirements.

